1 BACKGROUND AND RATIONALE

Peritoneal dialysis-related infection is one of the commonest reasons for patients to discontinue peritoneal dialysis (PD) therapy(1). Prevention of infection is of paramount importance for a successful PD programme. The catheter ESI can lead to tunnel tract infection and subsequently peritonitis, which is one of serious complications in PD(2,3). The International Society for Peritoneal Dialysis (ISPD) guidelines recommends regular application of topical antimicrobial agents, including mupirocin or gentamicin at the catheter exit-site to prevent ESI(4). However, the use of mupirocin has been reported to be associated with increased incidence of drug resistant micro-organisms(5–7). The mupirocin was used as the topical antimicrobial agents for exit-site care for PD patients in Singapore General Hospital before the period of 2013. However, the use of mupirocin was withdrawn from the hospital due to increasing evidence of methicillin-resistant *Staphylococcus aureus* (MRSA) which was attributed to the increased use of mupirocin cream(7). Similarly, the use of gentamicin was reported to have a trend towards increased incidence of fungal exit site infection (8). Hence, the alternative antimicrobial agent is warranted to prevent the ESI in PD patients

References

3. van Diepen ATN, Tomlinson GA, Jassal S V. The Association between Exit Site Infection and Subsequent Peritonitis among Peritoneal Dialysis Patients. *Clin J Am Soc Nephrol* [Internet]. 2012 Aug 1 [cited 2017 May 6];7(8):1266–71. Available from: <http://www.ncbi.nlm.nih.gov/pubmed/22745277>
4. Li PK-T, Szeto CC, Piraino B, de Arteaga J, Fan S, Figueiredo AE, et al. ISPD Peritonitis Recommendations: 2016 Update on Prevention and Treatment. *Perit Dial Int* [Internet]. Multimed Inc; 2016 [cited 2017 Mar 14];36(5):481–508. Available from: <http://www.ncbi.nlm.nih.gov/pubmed/27282851>

1.2 Rationale and Justification for the Study

1.2.1 Rationale for the Study Purpose

Catheter-related infection is one of the common reasons for peritoneal dialysis patients to discontinue PD therapy. The use of topical antibiotics cream at the catheter exit-site is recommended by International Society for Peritoneal Dialysis to prevent exit-site infection. However, the daily use of antibiotics cream at exit-site is reported to be associated with emergence of drug resistance organisms. Hence, the alternative antimicrobial agent (antiseptic) is needed to prevent exit-site infection in PD patients. In addition, the requirement of daily use of the cream by patients may potentially results in poor adherence to antibiotics application. Chlorhexidine is antiseptic agent and is active against both Gram-positive and Gram-negative organisms. The chlorhexidine-impregnated sponge dressing is required to change once a week only. There is no previous study on the role of chlorhexidine-impregnated sponge dressing in the prevention of exit-site infection in PD patients.

1.2.2 Rationale for Doses Selected

In the present study, the chlorhexidine impregnated sponge will be changed once every 7 days as previous randomized study showed non-inferiority of 7 days versus 3 days dressing change in prevention of catheter-related blood stream infection in critically ill adult patients (1)

1. Timsit, J.-F. *et al.* Chlorhexidine-impregnated sponges and less frequent dressing changes for prevention of catheter-related infections in critically ill adults: a randomized controlled trial. *JAMA* **301**, 1231–1241 (2009).

1.2.3 Rationale for Study Population

Incident peritoneal dialysis (PD) patients will be recruited in the study. This is to prevent the cross over effect of topical antibiotics in the prevalent PD patients.

1.2.4 Rationale for Study Design

The prospective cohort study is proposed as it is a pilot study only.

2 HYPOTHESIS AND OBJECTIVES

2.1 Hypothesis

We hypothesize that the use of weekly chlorhexidine-impregnated sponge dressing at the catheter exit site is safe and effective in the prevention of exit site infection in incident peritoneal dialysis patients

2.2 Primary Objectives

The primary aim of study is to examine the exit-infection rate in patients using chlorhexidine-impregnated sponge dressing.

2.3 Secondary Objectives

The secondary aim of the study is to examine the time to the first episode of exit-site infection, peritonitis rate, time to first episode of peritonitis, infection-related hospitalization, technique failure rate, mortality and adverse events and patient satisfaction with the use of chlorhexidine-impregnated sponge dressing

2.4 Potential Risks and Benefits:

2.4.1 Potential Risks

The common reported risk with use of chlorhexidine-impregnated sponge dressing is local skin irritation or contact dermatitis. The rare adverse event includes severe contact dermatitis which required removing the dialysis catheter, generalised allergic reactions and anaphylactic shock.

2.4.2 Potential Benefits

Chlorhexidine-impregnated sponge dressing can potentially be benefit for patients who are at high risk for exit site infection due to inability to clean the exit site daily including elderly, obese patients, patients with poor visual acuity etc. The use of weekly chlorhexidine-impregnated sponge dressing will also free patient from daily cleaning of exit site, which might provide extra-time for patients to enjoy other activities and potentially may improve the quality of life.

With the data collected from this pilot study, an adequately powered randomised controlled trial could be conducted to compare the effectiveness of once a week chlorhexidine-impregnated sponge dressing with daily topical anti-microbial cream in preventing exit site infection. If successful, our study has the potential to change current clinical practice and improve patient's outcomes.

3 STUDY POPULATION

3.1 List The Number and Nature of Subjects to be Enrolled.

Total of fifty incident peritoneal dialysis patients follow-up at Singapore General Hospital will be recruited for study.

3.2 Criteria for Recruitment and Recruitment Process

Potential participants will be referred by their treating physicians during admission to hospital for initiation of peritoneal dialysis or from clinic. The eligible patients will be approached by one of investigators for recruitment and informed consent will be taken from the patients.

3.3 Inclusion Criteria

All adult incident peritoneal dialysis patients between 21 to 90 years old, who are followed up in Singapore General Hospital

3.4 Exclusion Criteria

Patients with the following conditions will be excluded from the study

1. patients who have known history of allergy to chlorhexidine
2. patients who had previous history of peritoneal dialysis catheter exit-site infection
3. patients with mentally challenging conditions who are unable to give the valid consent for the study
4. patients who have been involved in the another study for exit site infection

3.5 Subject Replacement

There will be no replacement for participants who dropout from study for various reasons.

4 STUDY DESIGN

This a single centre, prospective cohort study.

4.1 Randomisation and Blinding

Not applicable

4.2 Contraception and Pregnancy Testing

Not applicable

4.3 Study Visits and Procedures

The participant will be followed up at 2, 6, 12, 24, 36 and 52 weeks of study and during each visit, the catheter exit-site will be examined by one of the investigators for any sign of infection or allergic reaction, and questionnaires about satisfaction with use of study material (biopatch) will be asked by a study team member at the 12 week of study. Each participant will be followed up for one year. After one-year of study period, there will not be additional follow-up for study purpose, however, participants will be continued followed up in SGH as per routine PD patients' schedule.

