4.4 Discontinuation/Withdrawal

4.4.1 Discontinuation Criteria

The participant will be discontinued from the study if he or she develops adverse effects related to the use of chlorhexidine-impregnated sponge dressing, which includes local cutaneous skin reaction at exit-site, contact dermatitis at exit-site or developed exit-site infection.

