4.4.2 Discontinuation Visit and Procedures

If participant is withdrawn from the study due to adverse effects, he/she will be treated as per routine recommended practice for the adverse event and will be scheduled to follow up in clinic. The frequency and interval of follow up will be depended on the clinical condition. If participant voluntarily withdrawal from the study, he/she will be followed up as per routine clinic schedule, which is once every 3 months.

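### Satisfaction is asked only at week 12 and not at discontinuation, so early stoppers are likely missed and the reported result is likely somewhat too favourable

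*Combined protocol and SAP*

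**What the plan says.** Section 2.3 lists "patient satisfaction with the use of chlorhexidine-impregnated sponge dressing" among the secondary outcomes. Section 4.3 sets visits at weeks 2, 6, 12, 24, 36 and 52 and places the satisfaction measure at one of them: "questionnaires about satisfaction with use of study material (biopatch) will be asked by a study team member at the 12 week of study". The same section states "Each participant will be followed up for one year".

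Section 4.4.1 discontinues a participant from the study for adverse effects of the dressing, with the reasons given as "local cutaneous skin reaction at exit-site, contact dermatitis at exit-site or developed exit-site infection". Under section 4.4.2, a participant withdrawn for adverse effects is "treated as per routine recommended practice for the adverse event and will be scheduled to follow up in clinic". For one who withdraws voluntarily, "he/she will be followed up as per routine clinic schedule, which is once every 3 months". Neither route includes a questionnaire.

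Nothing elsewhere fills the gap. The final visit (4.3.3) adds no study procedure. Appendix 1 lists only visit numbers and weeks. Section 9.2 gives no analysis for satisfaction and no handling of missing answers. Enrolment is fixed ("Total of fifty incident peritoneal dialysis patients", section 3.1), and section 3.5 adds: "There will be no replacement for participants who dropout from study for various reasons".

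**The concern.** Participants are examined at weeks 2 and 6 for infection and allergic reaction, and section 4.3.2 tells them to report discomfort or itching. A problem can therefore surface, and participation can end, before the only questionnaire. The stopping reasons in 4.4.1 are either harms of the dressing or the infection it is meant to prevent. Those missing at week 12 are thus selected by rule on experiences that plausibly lower satisfaction, and a summary of the remaining respondents would lean favourable.

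Convenience for the patient is part of the rationale (1.2.1 and 2.4.2), and section 2.4.2 says the pilot is meant to inform a randomised trial. The views of people who could not stay on the dressing are useful for planning that trial and are hard to recover later. A respondent count set against 50 would show how many are missing, but not what they thought.

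**Working it through.** **No figure to reproduce.** The plan states no satisfaction figure, satisfaction scale, dropout rate, exit-site infection rate or skin-stopping rate, and section 9.1 gives no sample size calculation. The size below is illustration only.

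**From the documents:** N = 50 (3.1); questionnaire at week 12 (4.3); planned follow-up 52 weeks (4.3).

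**Assumed:** a yes/no measure; p = 0.90 of continuers satisfied; q = 0.20, 0.50 or 0.90 of early stoppers satisfied; infection rate L = 0.2 or 0.4 per patient-year; skin stopping s = 0, 0.01 or 0.10.

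**Step 1: share lost before week 12.** Participants who stop in weeks 13 to 52 have already answered, so only the first 12 weeks count.

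If all skin stopping falls before week 12, d = 1 − exp(−L × 12/52) × (1 − s):

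- L = 0.2, s = 0: d = 0.0451, or 2.3 of 50
- L = 0.2, s = 0.01: d = 0.0547, or 2.7 of 50
- L = 0.4, s = 0.10: d = 0.1794, or 9.0 of 50

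If s is a one-year figure at constant hazard, d = 1 − exp(−(L − ln(1 − s)) × 12/52):

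- L = 0.2, s = 0.01: d = 0.0473, or 2.4 of 50
- L = 0.4, s = 0.10: d = 0.1101, or 5.5 of 50

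**Step 2: overstatement.** Satisfaction among all treated is (1 − d)p + dq, while the reported figure is p. The difference is d(p − q). With k lost, this is (k/50)(0.90 − q).

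| Lost before week 12 | q = 0.20 | q = 0.50 | q = 0.90 |
|---|---|---|---|
| 2 of 50 | 0.04 × 0.70 = 2.8 points | 0.04 × 0.40 = 1.6 | 0 |
| 3 of 50 | 0.06 × 0.70 = 4.2 | 0.06 × 0.40 = 2.4 | 0 |
| 5.5 of 50 | 0.11 × 0.70 = 7.7 | 0.11 × 0.40 = 4.4 | 0 |
| 9 of 50 | 0.18 × 0.70 = 12.6 | 0.18 × 0.40 = 7.2 | 0 |

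**Step 3: comparison with sampling error.** The 95% half-width is 1.96 × √(0.9 × 0.1/n): 8.5 points for n = 48, 8.6 for n = 47 and 9.2 for n = 41. Among the cases shown, only 9 lost with q = 0.20 exceeds it.

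**Plausibility of the inputs.** The package insert (Appendix 2) calls dermatitis and allergic reactions very rare, which points to the low cases for skin stopping. Section 2.4.1 calls local irritation or contact dermatitis the common reported risk, which points higher. In the cases of 2 or 3 lost, nearly all the loss comes from the assumed infection rate of 0.2 per patient-year, not from skin reactions.

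**The case against.** The strongest reply is that the text never restricts the questionnaire to current users. It is tied to week 12, section 4.3 promises a year of follow-up for each participant, and 4.4.2 keeps stoppers within reach: those with adverse effects are scheduled for clinic, and a three-month routine visit falls close to week 12. On that reading early stoppers could still be asked. This stands as a possibility, which is why the point is put as likely and not certain. But 4.4.1 removes these participants from the study itself and 4.4.2 gives them clinical follow-up only, so a site following the text would probably not ask them.

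Second, satisfaction among those still using the dressing after a common 12 weeks is a coherent quantity. It misleads only if presented as the view of everyone who started. That is right, and the remedy should keep this result.

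Third, adverse events and exit-site infections are outcomes in their own right, so the stops would be visible beside the satisfaction figure. This limits how far a reader could be misled, but does not supply the missing opinions.

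Fourth, every rate is assumed and the effect is mostly smaller than sampling error. Both are true. The case of 9 lost needs an infection rate of 0.4 per patient-year and 10% skin stopping, all before week 12, and should carry little weight. The direction is not guaranteed either: someone stopped for infection may still rate ease of use well.

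**Conclusion.** The concern holds, as a minor point worth considering. The plan asks about satisfaction once and schedules no questionnaire at discontinuation. Read as written, it likely loses the opinions of early stoppers for reasons tied to the outcome, and the result is likely somewhat too favourable. The size cannot be derived from the documents. With 2 or 3 of 50 lost it would be about 1.6 to 4.2 points under the stated assumptions, and it is zero if stoppers and continuers agree or if nobody stops before week 12. The outcome is descriptive with no decision rule, and the primary conclusion on exit-site infection is not affected. Confidence is medium, because it rests on the reading of 4.4.1 and on stoppers being less satisfied.

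**What to change.** In sections 4.3 and 4.4.2, state that the same questionnaire is given at week 12 or at discontinuation of the dressing, whichever comes first. For voluntary withdrawals, offer it at the next routine visit if they agree. Record weeks of use at the time of answering.

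Report respondents out of all who received a dressing, and show week-12 continuers and early stoppers separately, so that the common 12-week result is kept. Apply best-case and worst-case bounds only to those who still do not answer. On a yes/no measure each remaining non-respondent widens the bounds by 1/50, or 2 points.

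The cost is one line in each section. In the illustrations about 2 to 9 questionnaires move to the time of stopping, and participants stopped for adverse effects are already scheduled for clinic. The downsides are small: exposure varies among early stoppers, someone stopped in the first weeks has little use to rate, voluntary withdrawals are seen only every three months, and some may decline. No clinical rule changes.

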4.3.1 Screening Visits and Procedures

Potential participants will be referred by their treating physicians during admission to hospital for initiation of peritoneal dialysis or from clinic. Potential participants will be screened by one of investigators for recruitment and informed consent will be taken from the patients if eligible. No additional visit or additional blood test is needed for screening the participants.

4.3.2 Study Visits and Procedures

If potential participant is agreeable to participate in the study, the informed consent will be taken and participant will be taught how to use the chlorhexidine-impregnated sponge dressing by investigator. The chlorhexidine-impregnated sponge will be applied at the catheter exit-site. Participants will be observed for half an hour for anaphylactic reaction in the peritoneal dialysis centre after the application of chlorhexidine-impregnated dressing for the first time. Participants will be instructed to report any allergic reaction or discomfort or itchiness at the catheter exit-site. Participants will be instructed to change the sponge dressing at once a week, unless the dressing is soiled. Participant will be required to visit clinic at per schedule described above, and to be assessed by the investigator for any adverse effect and any sign of infection at catheter exit at each clinic visit.

4.3.3 Final Study Visit:

The final visit will be 52 week of study. There will be no additional procedure or instruction to participants with regards to the study during the final visit. However, participants will be taught

how to use the standard exit-site care as per centre protocol.

4.3.4 Post Study Follow up and Procedures

There will be no additional follow up for participants for study purpose. However, participants will be followed up as per routine clinic schedule for PD patients as per centre protocol.

4.4 Discontinuation/Withdrawal

4.4.1 Discontinuation Criteria

The participant will be discontinued from the study if he or she develops adverse effects related to the use of chlorhexidine-impregnated sponge dressing, which includes local cutaneous skin reaction at exit-site, contact dermatitis at exit-site or developed exit-site infection.

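### An exit-site infection or skin reaction takes the participant out of the study, not only off the dressing, and nothing says outcomes are still collected to one year

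*Combined protocol and SAP*

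**What the plan says.** Section 4.4.1 reads: "The participant will be discontinued from the study if he or she develops adverse effects related to the use of chlorhexidine-impregnated sponge dressing". The same sentence goes on to list the effects that are meant, and ESI is the last of them: "which includes local cutaneous skin reaction at exit-site, contact dermatitis at exit-site or developed exit-site infection". Section 4.4.2 then describes clinical care: "If participant is withdrawn from the study due to adverse effects, he/she will be treated as per routine recommended practice". On later visits it says only this: "The frequency and interval of follow up will be depended on the clinical condition". It names no study visit and no outcome to be recorded after the stop.

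Section 4.3 makes a general statement: "Each participant will be followed up for one year". Section 11 provides for monthly data collection. Neither says whether it still applies to a participant who has been discontinued.

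The secondary objectives in section 2.3 include "peritonitis rate, time to first episode of peritonitis, infection-related hospitalization, technique failure rate, mortality". Section 1 states: "The catheter ESI can lead to tunnel tract infection and subsequently peritonitis". Section 1.2.1 adds that catheter-related infection is a common reason for leaving peritoneal dialysis (PD).

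Section 9.2 plans Poisson regression for the ESI rate and Cox and Kaplan-Meier methods for the times to first ESI and to peritonitis. It also plans a comparison of the ESI rate with a historical cohort. It gives no censoring rule and does not say how either cohort's episodes are counted.

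**The concern.** Two things are left open.

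**Follow-up after the stop.** The rule ends study participation rather than use of the dressing. If data end there, they end at the event after which, on the protocol's own rationale, peritonitis and loss of PD become more likely. Kaplan-Meier and Cox methods assume that censoring carries no information about later risk, and censoring at ESI can break that for peritonitis and technique failure. The resulting rates would describe time on the dressing rather than one year. Section 2.4.2 intends the pilot's data to support a randomised trial, and its planners need to know which rate they have.

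**Which ESIs trigger the stop.** ESI is listed among adverse effects related to the dressing. That can mean every ESI, or only an ESI judged related. If every ESI counts, each participant contributes at most one episode and the primary rate is a first-episode rate. If only some count, the rate mixes first and repeat episodes. The comparison with the historical cohort needs the same rule on both sides.

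**Working it through.** The plan has no expected rate, event count or sample-size calculation (section 9.1), so there is no figure of its own to reproduce. From the documents: 50 participants (section 3.1), one year each (section 4.3), no replacement (section 3.5). **Every rate below is assumed.**

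**1. Stops and patient-years after the stop.** Let L be the ESI rate (0.3 per patient-year, range 0.1 to 0.5), p the share of ESIs that trigger the stop, and 0.1 the rate of skin-reaction stops. Then s = pL + 0.1.

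- Stops before week 52 = 50 × (1 − e^−s)
- On-dressing patient-years = 50 × (1 − e^−s)/s
- Patient-years after the stop = 50 minus that

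For p = 1 and L = 0.3, s = 0.4: stops = 50 × 0.3297 = 16.5; on-dressing = 16.48/0.4 = 41.2; after the stop = 8.8.

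| ESI rate | Stops, every ESI | Years after stop | Stops, half of ESIs | Years after stop |
|---|---|---|---|---|
| 0.1 | 9.1 | 4.7 | 7.0 | 3.6 |
| 0.3 | 16.5 | 8.8 | 11.1 | 5.8 |
| 0.5 | 22.6 | 12.4 | 14.8 | 7.8 |

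With a further assumed 0.2 per year of other exits (death, transplant, transfer off PD), total follow-up is 50 × (1 − e^−0.2)/0.2 = 45.3 patient-years. Of these, 7.7 (4.1 to 10.9) fall after the stop if every ESI counts, and 5.1 (3.1 to 6.9) if half do.

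**2. Peritonitis rate if every ESI ends data collection.** Assume a baseline of 0.25 per year, multiplied by HR for w years after each ESI, and the same ESI rate on and off the dressing. All recorded time then precedes any ESI, so the recorded rate is 0.25. The share of the year spent in a post-ESI window is

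f = [w − (1 − e^−Lw)/L] + (1 − w)(1 − e^−Lw).

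The full-year rate is 0.25 × (1 + (HR − 1)f), and the understatement is 1 − 1/(1 + (HR − 1)f), which does not depend on the 0.25.

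For L = 0.3, HR = 5 and 60 days, f = 0.044. The full-year rate is 0.25 × (1 + 4 × 0.0442) = 0.294, and the understatement is 15%.

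| HR, window | ESI 0.1 | ESI 0.3 | ESI 0.5 |
|---|---|---|---|
| 1 | 0% | 0% | 0% |
| 2, 30 days | 0.8% | 2.3% | 3.7% |
| 3, 30 days | 1.5% | 4.5% | 7.2% |
| 5, 30 days | 3.0% | 8.5% | 13.4% |
| 5, 60 days | 5.6% | 15.0% | 22.5% |
| 10, 60 days | 11.9% | 28% | 39.5% |

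If half of ESIs trigger the stop, simulation of 200,000 participants at ESI 0.3, HR 5 and 60 days gives 7.5% (0.272 against 0.294). Peritonitis that presents with the ESI and is recorded at the stop would shrink all these figures.

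**3. Against sampling error.** 0.25 × 41.2 is about 10 episodes. Ten in 41.2 patient-years is 0.24 per year, exact 95% interval 0.12 to 0.45, which contains 0.294.

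**4. Primary ESI rate.** If every ESI triggers the stop, L = 0.3 yields 0.3 × 41.2 = 12.4 episodes in 41.2 patient-years, which is again 0.3. With constant, equal risk and person-time ending at the event, the first-episode rate equals the all-episode rate. If half trigger it, the chance of two or more counted ESIs is 0.3 × 0.5 × (0.3/0.4) × [(1 − e^−0.4)/0.4 − e^−0.4] = 0.0173, or about 0.9 of 50 participants.

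**The case against.** The best reply is that nothing says data collection ends. Section 4.3 promises one year for each participant, section 11 has monthly collection, and section 4.4.2 keeps withdrawn participants in clinic. The consent pages are not in the copy reviewed, so wording on data after withdrawal cannot be called absent. This stands as far as it goes: loss of data is a possibility, not a fact. But none of these sections says that it applies after discontinuation, and section 4.3 taken literally conflicts with section 4.4.1.

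A second reply is that on-dressing rates are the target. Section 2.2 refers to patients using the dressing, and section 2.3 closes with a phrase about its use that may cover the whole list or only satisfaction. This is arguable, and it is a reason to keep the primary rate on-dressing. It does not make censoring at ESI harmless for the peritonitis and technique-failure analyses.

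A third is that this is a 50-patient pilot without a control arm, and the shift is lost in the noise. At the central assumption that is right. A confidence interval shows sampling error, however; it does not tell the reader which period a rate covers.

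A reader might also take section 4.3.4, "There will be no additional follow up for participants for study purpose", as confirming that discontinued participants are not followed. It does not: it follows the week-52 final visit and concerns the time after the study year, so it is no part of the conflict.

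**Conclusion.** The point holds as an unreconciled rule with a possible informative loss of secondary outcome data, and it should be fixed. Sections 4.4.1 and 4.4.2 remove participants from the study, section 4.3 promises a year, and nothing states what is collected in between.

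On the assumed rates, about 9 to 23 of 50 participants stop if every ESI counts (5 to 12 patient-years after the stop), and about 7 to 15 if half do (4 to 8 patient-years). If every ESI counts, understatement of peritonitis runs from 0%, if risk does not rise after ESI, to about 40% at the extreme of the settings tried. The documents say only that ESI can lead to peritonitis, so no single percentage in that range can be put forward as the expected effect.

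Two stronger conclusions might be inferred and are not supported. One is that the primary ESI rate is biased: with constant, equal risk and person-time ending at the stop it is not, and the need is for a label and a matching historical counting rule. The other is that every secondary outcome is distorted in a known direction: none is shown for mortality, or after stops for skin reactions.

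**What to change.** Leave the rule for stopping the dressing unchanged. Then:

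- Reconcile sections 4.3, 4.4.1 and 4.4.2 so that stopping the dressing does not end outcome collection, and state which ESIs section 4.4.1 covers.
- Subject to consent, collect outcomes from clinic and PD-centre records to week 52. Collect ESI and peritonitis until death, transfer off PD or transplant if earlier. Collect infection-related hospitalisation, technique failure and death to week 52 regardless of transfer or transplant.
- Keep the on-dressing ESI rate as primary, with person-time ending at the stop. Label it first-episode if every ESI triggers the stop, and apply the same counting rule to the historical cohort in section 9.2.
- Report peritonitis and technique failure over full follow-up. If an on-dressing rate is also shown, label it as such.

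The cost is one amendment notified to the review board (section 12), any consent wording needed, a short addition to section 9.2, and record abstraction for roughly 7 to 23 participants (about 4 to 12 patient-years) on the assumed rates. The drawback is less regular ascertainment after the stop, because section 4.4.2 ties the clinic interval to the patient's condition.
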